**15.29 Nursing Guidelines:**

- Myelosuppression is dose-dependent and reversible with treatment interruption and/or dose reduction. Monitor CBC w/diff regularly. Instruct patient to report any unusual bruising or bleeding (thrombocytopenia); signs and symptoms of infection (neutropenia); and energy conserving lifestyle (anemia).
- Lenalidomide can have thrombotic adverse events (i.e DVT and PE). Instruct patient to report any limb swelling or pain, and to seek medical attention for shortness of breath or chest pain.
- Because of the potential for birth defects patients should be instructed in effective methods of birth control. Female patients should use 2 forms of birth control during treatment and for 4 weeks after discontinuing therapy. Males must be instructed to use a latex condom during any sexual contact with a woman of child bearing potential (even if they have had a vasectomy), because it is unknown if lenalidomide is present in semen.
- Patients may experience pruritus, rash and dry skin. Because of the rare risk of Steven's Johnson Syndrome, patients should immediately report any rash to their provider.
- Drug may cause hyperglycemia. Patients with diabetes or impaired fasting glucose may need to have their glucose levels monitored more closely.
- Gastrointestinal side effects (diarrhea, constipation, nausea, dyspepsia, anorexia, etc) are commonly seen. Manage patient symptomatically and monitor for effectiveness.
- Patients may experience myalgias, arthralgias, parasthesias and other generalized pain. Administer analgesics as ordered and monitor for their effectiveness. Rarely infective bursitis and arthritis have been reported. Instruct patients to report any joint pain or redness to study team immediately.
- Upper respiratory symptoms (nasopharyngitis, cough, epistaxis, etc.) can be seen. Manage symptomatically and monitor for effectiveness.
- Agent may cause fatigue, dizziness, vertigo or blurred vision. Instruct patients to use caution when driving or operating machines.
- Monitor LFT's and report any elevations to the study team. Instruct patient to report abdominal pain and/or jaundice to the study team.
- All prescribers and patients must be enrolled into the REVOLIMID REMS program. Only enough lenalidomide for one cycle of therapy will be supplied to the patient each cycle.

- Rarely secondary malignancies have been seen after lenolidamide therapy, including MDS, squamous/basal cell carcinomas of the skin, T-cell type acute leukemia.
- Monitor Renal function, renal failure has been reported.

### 15.3 Dexamethasone for Oral Administration

15.31 **Background:** Dexamethasone is an adrenal corticosteroid compound. Dexamethasone decreases inflammation by suppression of neutrophil migration, decreased production of inflammatory mediators, and reversal of increased capillary permeability; suppresses normal immune response. Dexamethasone's mechanism of antiemetic activity is unknown.

15.32 **Formulation:** Commercially available for oral administration as:  
Tablets [scored]: 0.5 mg, 0.75 mg, 1 mg, 1.5 mg, 2 mg, 4 mg, and 6 mg  
Solution, oral: 0.5 mg/mL (500 mL)  
Solution, oral concentrate: Dexamethasone Intensol: 1 mg/mL (30 mL)

15.33 **Preparation, storage, and stability:** Refer to package insert for complete preparation and dispensing instructions. Store oral tablets at room temperature between 20°C to 25°C (60°F to 77°F). Protect from moisture. Dispense in a well-closed, light-resistant container as defined in the USP/NF. Store oral liquid at room temperature, do not freeze. Do not use if solution contains a precipitate. Refer to commercial package for drug expiration date.

15.34 **Administration:** Refer to the treatment section for specific administration instructions. May be taken with meals to decrease GI upset.

15.35 **Pharmacokinetic information:**  
**Onset of action:** Prompt  
**Duration of metabolic effect:** 72 hours  
**Metabolism:** Hepatic  
**Half-life elimination:** Normal renal function: 1.8-3.5 hours; **Biological half-life:** 36-54 hours  
**Time to peak, serum:** Oral: 1-2 hours  
**Excretion:** Urine and feces

15.36 **Potential Drug Interactions:**  
**Cytochrome P450 Effect: Substrate of CYP3A4 (major); Induces CYP2A6** (weak), 2B6 (weak), 2C8 (weak), 2C9 (weak), 3A4 (strong)  
**Increased Effect/Toxicity:** Aprepitant, azole antifungals, calcium channel blockers, cyclosporine, estrogens, and macrolides may increase the serum levels of corticosteroids. Corticosteroids may increase the hypokalemic effects of amphotericin B or potassium-wasting diuretics (loop or thiazide); monitor. Refer to the package insert for a listing of other drugs.  
**Decreased Effect:** Antacids and bile acid sequestrants may reduce the absorption of corticosteroids; may reduce the absorption of corticosteroids; separate

administration by 2 hours. Aminoglutethimide, barbiturates, and CYP3A4 inducers may reduce the serum levels/effects of dexamethasone and dexamethasone may decrease the levels/effects of other CYP3A4 substrates. Serum concentrations of isoniazid may be decreased by corticosteroids. Corticosteroids may lead to a reduction in warfarin effect. Corticosteroids may suppress the response to vaccinations.

**Ethanol/Nutrition/Herb Interactions:**

Ethanol: Avoid ethanol (may enhance gastric mucosal irritation).

Food: Dexamethasone interferes with calcium absorption. Limit caffeine.

Herb/Nutraceutical: Avoid cat's claw (*Uncaria tomentosa*), echinacea (have immunostimulant properties)

15.37 **Known potential adverse events:** Consult the package insert for the most current and complete information.

**Common known potential toxicities**, frequency not defined:

Fluid and electrolyte disturbances, congestive heart failure in susceptible persons, hypertension, euphoria, personality changes, insomnia, exacerbation of infection, exacerbation or symptoms of diabetes, psychosis, muscle weakness, osteoporosis, vertebral compression fractures, pancreatitis, esophagitis, peptic ulcer, dermatologic disturbances, convulsions, vertigo and headache, endocrine abnormalities, ophthalmic changes, and metabolic changes. Some patients have experienced itching and other allergic, anaphylactic or hypersensitivity reactions. Withdrawal from prolonged therapy may result in symptoms including fever, myalgia and arthralgia.

15.38 **Drug procurement:** Commercial supplies. Pharmacies or clinics shall obtain supplies from normal commercial supply chain or wholesaler.

15.4 Daratumumab (Darzalex®)

Please consult the most current Investigator's Brochure and package insert for complete drug information.

15.41 **Background:** Daratumumab is an immunoglobulin G1 kappa (IgG1κ) human monoclonal antibody against CD38 antigen, produced in a mammalian cell line (Chinese Hamster Ovary [CHO]) using recombinant DNA technology. The molecular weight of daratumumab is approximately 148 kDa.

CD38 is a transmembrane glycoprotein (48 kDa) expressed on the surface of hematopoietic cells, including multiple myeloma and other cell types and tissues and has multiple functions, such as receptor mediated adhesion, signaling, and modulation of cyclase and hydrolase activity. Daratumumab is an IgG1κ human monoclonal antibody (mAb) that binds to CD38 and inhibits the growth of CD38 expressing tumor cells by inducing apoptosis directly through Fc mediated cross linking as well as by immune-mediated tumor cell lysis through complement dependent cytotoxicity (CDC), antibody dependent cell mediated cytotoxicity (ADCC) and antibody dependent cellular phagocytosis (ADCP). Myeloid derived suppressor cells (MDSCs) and a subset of regulatory T cells (CD38+Tregs) expresses CD38 and is susceptible to daratumumab mediated cell lysis.

**15.42 Formulation:**

IV formulation: Daratumumab IV solution is a colorless to yellow liquid and sterile concentrate of 20 mg/mL in a vial with a nominal fill of 5 mL or 20mL. It will be manufactured and provided under the responsibility of Janssen Biotech. Refer to the Product Insert for a list of excipients.

**15.43 Preparation and storage:**

IV drug formulation: Daratumumab is supplied in glass vials containing daratumumab at a concentration of 20 mg/mL. Study drug labels will contain information to meet the applicable regulatory requirements. Each vial will contain a study-specific label with a unique identification number.

All study drug vials must be stored in the original carton in a refrigerator ranging from 2°C to 8°C and must not be utilized after the expiry date printed on the label. The product must be protected from light and must not be frozen. Daratumumab does not contain preservatives; therefore, any unused portion remaining in the vial must be discarded.

Daratumumab will be diluted in a sterile, pyrogen-free physiological saline solution (0.9% NaCl) prior to IV administration. Refer to Section 7 of the protocol, the Investigational Product Preparation Instructions or Investigational Product Procedures Manual for details regarding dose preparation, storage, and handling of diluted solutions.

**15.44 Administration:**

IV administration: Administer the diluted solution by intravenous infusion using an infusion set fitted with a flow regulator and with an in-line, sterile, non-pyrogenic, low protein-binding polyethersulfone (PES) filter (pore size 0.22 or 0.2 micrometer). Polyurethane (PU), polybutadiene (PBD), PVC, PP or PE administration sets must be used.

- Infusion should be completed within 15 hours.
- Do not store any unused portion of the infusion solution for reuse. Any unused product or waste material should be disposed of in accordance with local requirements.
- Do not infuse **daratumumab** concomitantly in the same intravenous line with other agents.

**15.45 Pharmacokinetic information for IV administration:**

The pharmacokinetics (PK) of daratumumab following intravenous administration were evaluated in patients with relapsed and refractory multiple myeloma at dose levels from 0.1 mg/kg to 24 mg/kg, and included the recommended 16 mg/kg dose and regimen. Over the dose range from 1 to 24 mg/kg, increases in area under the concentration-time curve (AUC) were more than dose-proportional. Clearance decreased with increasing dose and repeated dosing, indicating target-mediated pharmacokinetics. The mean (SD) predose (trough) serum concentration at the end of weekly dosing was 573 (332) µg/mL.

The half-life of daratumumab is both concentration and time dependent. After the first dose of 16 mg/kg of daratumumab, the observed half-life was 9±4 days. The model-derived half-life associated with linear elimination was approximately 18±9 days; this is the half-life that can be expected following repeat dosing of

daratumumab. Apparent steady state seems to be reached approximately 5 months into the every 4 weeks dosing period of the 16 mg/kg with a schedule of weekly for 8 weeks, every 2 weeks for 16 weeks, and then every 4 weeks thereafter (approximately 11 months of treatment in total).

As expected with subcutaneous administration, concentration-time curves following administration in all cohorts indicate a later  $T_{max}$  of approximately 72h post-dose, compared with IV administration when  $T_{max}$  occurs at or near the end of infusion. The range of C3D1  $C_{trough}$  observations for the SC cohort is within the range observed following 16 mg/kg IV dosing, and the variability appeared to be similar for the daratumumab SC and 16 mg/kg IV cohorts. The observed  $C_{max}$  values from the daratumumab SC cohort is within the range observed for daratumumab 16 mg/kg IV.

### ***Special Populations***

**Renal Impairment:** The population PK analysis included 71 patients with normal renal function (creatinine clearance [CrCL]  $\geq$ 90 mL/min), 78 patients with mild renal impairment (CrCL <90 and  $\geq$ 60 mL/min), 68 patients with moderate renal impairment (CrCL <60 and  $\geq$ 30 mL/min), and 6 patients with severe renal impairment or end stage renal disease (CrCL <30 mL/min). No clinical differences in exposure to daratumumab were observed between patients with renal impairment and those with normal renal function.

**Hepatic Impairment:** The population PK analysis included 189 patients with normal hepatic function (TB and AST  $\leq$ ULN) and 34 with mild hepatic impairment (TB 1.0 $\times$  to 1.5 $\times$  ULN or AST>ULN) patients. No clinical differences in the exposure to daratumumab were observed between patients with mild hepatic impairment and those with normal hepatic function. Daratumumab has not been studied in patients with moderate (TB>1.5 $\times$  to 3 $\times$  ULN and any AST) or severe (TB>3 $\times$  ULN and any AST) hepatic impairment.

**15.46 Potential Drug Interactions:** No drug interaction studies have been performed.

**15.47 Known potential toxicities:**

Very common known potential toxicities,  $\geq$  10%:

Injury, poisoning, and procedural complications: infusion related reaction

Infections and infestations: pneumonia, upper respiratory tract infection, bronchitis, pneumonia

Blood and lymphatic system disorders: neutropenia, thrombocytopenia, anemia, lymphopenia

Vascular disorders: hypertension

Nervous system disorders: headache, peripheral sensory neuropathy

Respiratory, thoracic, and mediastinal disorders: cough, dyspnea

Gastrointestinal disorders: nausea, vomiting, diarrhea

Musculoskeletal and connective tissue disorders: muscle spasms

General disorders and administration site conditions: fatigue, pyrexia, peripheral edema

Common known potential toxicities, 1% - <10%:

Injury, poisoning, and procedural complications: infusion related reaction

Infections and infestations: respiratory tract infection, influenza, lower respiratory tract infection, sepsis, sinusitis, rhinitis, pharyngitis, viral respiratory tract infection, tonsillitis, lung infection, herpes zoster  
Blood and lymphatic disorders: febrile neutropenia,  
Cardiac disorders: atrial fibrillation  
Respiratory, thoracic, and mediastinal disorders: pulmonary edema, hypoxia, laryngeal edema, pneumonitis, bronchospasm  
Gastrointestinal disorders: diarrhea

Uncommon and rare known potential toxicities, <1%:  
Infections and infestations: metapneumovirus infection, tracheitis, acute sinusitis, bronchiolitis, epiglottitis, oropharyngeal candidiasis, tracheobronchitis, upper respiratory tract infection bacterial, bronchitis bacterial, respiratory syncytial virus infections, laryngitis, streptococcal pharyngitis, viral rhinitis  
Blood and Lymphatic Disorders: neutropenic sepsis, neutropenic infection  
Please refer to the Investigator Brochure for a more comprehensive list of treatment-emergent adverse events.

15.48 **Drug procurement:** Daratumumab (Darzalex®) will be provided to research subjects for the duration of their participation in this trial at no charge to them or their insurance providers.

15.49 **Nursing Guidelines:**

- Daratumumab can cause severe infusion reactions, usually during the first infusion. Patients who have experienced a reaction may experience further reactions with subsequent infusions. Most reactions occur during or within 4 hours of infusion, however may occur up to 48 hours after an infusion. Warn patient of this possibility. Monitor patient throughout infusion for bronchospasm, hypoxia, SOB, and hypertension. Patients may also experience symptoms of anaphylaxis. Administer emergency medication as ordered.
- Patients may experience infections, including URI and pneumonia. Patients who have an ongoing infection should not receive agent.
- Patients may experience gastrointestinal side effects including diarrhea and nausea. Treat symptomatically and monitor for effectiveness.
- Warn patients about the possibility of peripheral neuropathy, dizziness, and insomnia.
- Fatigue is common. Instruct patient in energy conserving lifestyle.
- Rarely patients may experience cardiac issues including, atrial-fibrillation, peripheral edema, and hypertension. Instruct patient to report any chest pain, heart palpitations, and swelling to the study team.

15.5 Dexamethasone commercial supply for Infusion Administration

- 15.51 Formulation and storage: Dexamethasone sodium phosphate is supplied as 4mg/ml IV solution in 5ml vials. Store intact vials at controlled room temperature, do not refrigerate. Protect from heat and light.
- 15.52 Preparation: The sterile solution from the vial may be further diluted in D5W or NS (refer to the treatment section of the protocol).
- 15.53 Stability: Refer to expiration date on the vial.
- 15.54 Administration: IV push or infusion (see treatment section of the protocol).
- 15.55 Known potential toxicities: Fluid and electrolyte disturbances, congestive heart failure in susceptible persons, hypertension, euphoria, personality changes, insomnia, exacerbation of infection, exacerbation or symptoms of diabetes, psychosis, muscle weakness, osteoporosis, vertebral compression fractures, pancreatitis, esophagitis, peptic ulcer, dermatologic disturbances, convulsions, vertigo and headache, endocrine abnormalities, ophthalmic changes, and metabolic changes. Some patients have experienced itching and other allergic, anaphylactic or hypersensitivity reactions. Withdrawal from prolonged therapy may result in symptoms including fever, myalgia and arthralgia.
- 15.56 Drug procurement: Commercially available from several commercial sources.
- 15.57 **Nursing guidelines:**
  - 15.571 Monitor regularly for hypertension, CHF, and other evidence of fluid retention.
  - 15.572 Advise patient of possible mood or behavioral changes, i.e., depression, euphoria, insomnia, even psychosis. Instruct patient to report any suspected changes to healthcare team.
  - 15.573 Assess for symptoms of gastric ulcer, heartburn, or gastritis. Suggest antacids. Instruct patient to report symptoms to healthcare team if unable to control.
  - 15.574 Evaluate signs of infection, particularly local candidal infections and treat appropriately.
  - 15.575 Monitor blood glucose frequently.
  - 15.576 Instruct patient to report frequent unrelenting headaches or visual changes to healthcare team.
  - 15.577 Advise patient that easy bruising is a side effect.

## 16.0 Statistical Considerations and Methodology

### 16.1 Overview

This study is designed to assess the confirmed complete response rate with daratumumab added to ixazomib, lenalidomide and dexamethasone, when used as initial therapy in patients with previously untreated symptomatic MM using a one-stage binomial phase II study design in each arm. This study will include 2 treatment arms: Arm A (Dexamethasone cycles 1-12) and Arm B (Dexamethasone cycles 1-2 only).

### 16.11 Primary Endpoint

The primary endpoint in each arm of this trial is the confirmed complete response rate. A confirmed complete response is defined as objective status of CR or sCR that is maintained on two consecutive evaluations at least 2 weeks apart. All patients meeting the eligibility criteria, who have signed a consent form and have begun treatment will be evaluable for response, unless they are determined to be a major violation.

### 16.12 Sample Size

The one-stage binomial design to be used in each arm is fully described below. A maximum of 36 evaluable patients will be accrued to each arm of this phase II study unless undue toxicity is encountered. We anticipate accruing an additional 4 patients in each arm to account for ineligibility, cancellation, major treatment violation, or other reasons for a maximum of 40 patients accrued in each arm, and 80 patients overall.

### 16.13 Accrual Rate and Study Duration

The anticipated accrual rate is 3 evaluable multiple myeloma patients per month, translating to a duration of approximately one year for accrual in each arm. Accrual to Arm A will be completed before accrual is opened to Arm B. In each arm, the total duration before any results may be available is expected to be approximately 1.5 years from the date of activation for that arm, or until the last patient accrued to that arm has been observed for at least 6 months. The maximum total study duration is expected to be 5 years, or until the last patient accrued has been followed for 3 years.

### 16.2 Statistical Design (to be evaluated in each arm independently)

#### 16.21 Decision Rule

In a prior phase I/II study of previously untreated multiple myeloma patients, the efficacy of a combination of ixazomib, lenalidomide and dexamethasone was evaluated. A total of 53 patients were treated at the recommended phase II dose of 4.0 mg ixazomib, where a complete response rate of 27% was seen. This study will add daratumumab to the combination of ixazomib, lenalidomide and dexamethasone. An increase in complete response rate with this four-drug combination would be of interest.

The largest success proportion where the proposed treatment regimen would be considered ineffective in this population is 25%, and the smallest success proportion that would warrant subsequent studies with the proposed regimen in this patient population is 45%. The following one-stage binomial design requires 36 evaluable patients to test the null hypothesis that the true success proportion in this patient population is at most 25%.

16.211 Final Decision Rule: Enter 36 evaluable patients into the study. If 12 or fewer successes are observed in the first 36 evaluable patients, we will consider this regimen ineffective in this patient population. Otherwise, if the number of successes is at least 13, this will be considered evidence of promising activity and the treatment may be recommended for further testing in subsequent studies.

16.212 Over Accrual: If more than the target number of patients are accrued, the additional patients will not be used to evaluate the final decision rule or used in any decision making process. Analyses involving over accrued patients are discussed in Section 16.313.

16.22 Power and Significance Level: Assuming that the number of successes is binomially distributed, the significance level is .09, i.e. there is a 9% chance of finding the drug to be effective when it truly is not. The probability of declaring that this regimen warrants further study (i.e. statistical power) under various success proportions can be tabulated as a function of the true success proportion as shown in the following table.

If the true success proportion is...	0.25	0.30	0.35	0.40	0.45
Then the probability of declaring that the regimen warrants further study is...	0.09	0.26	0.51	0.74	0.89

16.23 Other considerations: Adverse events, quality/duration of response, and patterns of treatment failure observed in this study, as well as scientific discoveries or changes in standard care will be taken into account in any decision to terminate the study

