***Newly Diagnosed Multiple Myeloma (C16005):***

In Study C16005, ixazomib is given weekly (Days 1, 8, and 15), in combination with lenalidomide (Days 1-21), and dexamethasone (Days 1, 8, 15, and 22) in a 28-day cycle. Patients with newly diagnosed MM were enrolled and treated with oral ixazomib (days 1, 8, and 15) plus lenalidomide 25 mg (days 1-21) and dexamethasone 40 mg (days 1, 8, 15, 22) for up to twelve 28-day cycles, then maintenance therapy with ixazomib (same schedule) every 28 days until progression. Patients were allowed to undergo stem cell collection after 3 cycles and discontinue for autologous stem cell transplant (ASCT) after 6 cycles. Overall, 65 patients were enrolled, 15 in Phase 1 and 50 in Phase 2. Patients received a median of 6 cycles (range 1-19) with 27 (42%) remaining on treatment as of November 2012. Of those who have undergone stem cell mobilization, a median yield was  $11.3 \times 10^6$  CD34+ cells/Kg (range 5-28). ixazomib MTD was established as 2.97 mg/m^2 and RP2D was selected as 2.23 mg/m^2; RP2D translates to a 4.0 mg fixed dose based on population PK results. Among the 64 evaluable patients, the overall response rate was 92%, including 55% VGPR and 23% CR (Figure 3 below). Median time to first response was 0.92 months (range 0.89-6.44).

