The most common (>25%) TEAEs included neutropenia (81%), muscle spasms (44%), cough (38%), diarrhea (34%), fatigue and hypertension (28% each). Eighteen (56%) patients had IRRs and these were generally mild to moderate and occurred mostly during the first cycle. IRRs included cough (25%), allergic rhinitis, nausea, and vomiting (9% each), as well as dyspnea, nasal congestion, and hypertension (6% each). The overall response rate was 88%, with 11 (34%) partial responses and 17 (53%) ≥very good partial responses (VGPRs) that included 7 (22%) stringent complete responses, 1 (3%) complete response, and 9 (28%) VGPRs. The median time to first and best response was 1 month and 4.5 months, respectively. Results of this study confirm the efficacy of combining daratumumab with lenalidomide and dexamethasone. A large phase 3 trial of Daratumumab and Rd versus Rd has completed accrual.

**1.6 Rationale for the current trial:** Ixazomib in combination with lenalidomide and dexamethasone results in high response rates and deep responses in patients with newly diagnosed myeloma. It is well tolerated and patients are able to stay on it long term as a maintenance therapy. More recently, addition of daratumumab to lenalidomide and dexamethasone has resulted in significant activity in relapsed myeloma. The combination of the ixazomib, lenalidomide, daratumumab and dexamethasone presents the potential to further enhance the response to therapy with four different drug classes with no significant overlapping toxicities. We hypothesize that this combination will lead to deep response including a higher proportion of MRD negative disease that will translate into longer survival in these patients.

**Rationale for Arm B:** Long term therapy with dexamethasone is associated with various side effects including osteoporosis, adrenal suppression, muscle weakness, and increased risk of opportunistic infections. Given the efficacy of the daratumumab, ixazomib and lenalidomide, it is likely we will be able to decrease the dexamethasone doses and potentially eliminate it after the initial cycles. We will add a similar cohort of patients and treat them with dexamethasone only for the first two cycles of treatment and then discontinue. The endpoints of the trial will not be altered.

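### Is the stated 9% false-positive rate too low because the 25% null sits below the cited 27% complete response rate?

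*Combined protocol and SAP*

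**What the plan says.** Section 16.21 starts from an earlier phase I/II study of the three-drug combination. It reports 53 patients at the 4.0 mg ixazomib dose, "where a complete response rate of 27% was seen", and adds: "An increase in complete response rate with this four-drug combination would be of interest".

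The next paragraph fixes the design values. "The largest success proportion where the proposed treatment regimen would be considered ineffective in this population is 25" per cent, and the rate that would justify further study is 45%. The 36 evaluable patients are there to "test the null hypothesis that the true success proportion in this patient population is at most 25" per cent. Twelve or fewer successes means ineffective; 13 or more means promising.

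Section 16.22 gives a significance level of .09, explains it as "there is a 9% chance of finding the drug to be effective when it truly is not", and tabulates the pass probability at true rates of 0.25, 0.30, 0.35, 0.40 and 0.45. The same design is applied to each arm separately.

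**The concern.** The section names one benchmark, 27%, says that an increase is what matters, and then tests against a lower rate without explanation. A reader could take a drug that is truly not effective to mean that daratumumab adds nothing to the three-drug backbone. On the section's own benchmark that is a true rate of 27%, which lies just outside the null. The 9% does not bound the error there, and the table steps from 0.25 to 0.30 without showing it.

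There is no concurrent three-drug control, since both arms contain daratumumab. The stated error rate is therefore a main guide to how often an addition of no value would be called promising. If the relevant figure were nearer 15%, an Arm A result of 13 or 14 responders would deserve more caution than the 9% suggests.

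**Working it through.** **Inputs.** From 16.21: n = 36 evaluable patients, pass if X ≥ 13, null rate 0.25, alternative 0.45, and a cited rate of 27% in 53 patients. From the account of study C16005 in Section 1.3: "Among the 64 evaluable patients, the overall response rate was 92%, including 55% VGPR and 23% CR".

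**Formula.** With X binomial, P(pass | p) = P(X ≥ 13) = Σ C(36, k) p^k (1 − p)^(36 − k), summed over k = 13 to 36.

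**Step 1: reproduce the plan's table.**

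| True rate | Computed P(X ≥ 13) | Section 16.22 |
|---|---|---|
| 0.25 | 0.0922 | 0.09 |
| 0.30 | 0.2635 | 0.26 |
| 0.35 | 0.5068 | 0.51 |
| 0.40 | 0.7385 | 0.74 |
| 0.45 | 0.8933 | 0.89 |

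All five entries agree to two decimals. The neighbouring cut-offs do not give 0.09 at 25%: ≥ 12 gives 0.167 and ≥ 14 gives 0.046.

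**Step 2: the benchmark rates.**

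- At 27%: 0.1485, which is 0.1485 / 0.0922 = 1.6 times the stated level.
- At 14/53 = 26.4%: 0.130.
- At 23%: 0.052.

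**Step 3: what the printed table already tells a reader.** Linear interpolation at 0.27 gives 0.09 + (0.02/0.05) × (0.26 − 0.09) = 0.158, close to the exact 0.149.

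**Step 4: how firm the 27% is.** No whole number out of 53 rounds to 27% (14/53 = 26.4%, 15/53 = 28.3%), so the count is an assumption. With 14/53 the exact (Clopper-Pearson) 95% interval is 15.3% to 40.3%, which includes 25%. Putting those limits through the rule gives pass probabilities of about 0.2% and 75%. The evidence behind the 27% cannot separate 25% from 27%. The two reported point estimates, 23% and 27%, average (23 + 27)/2 = 25%.

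**Step 5: whether 27% is the right no-effect rate here.**

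- *Endpoint.* Section 16.11 requires an "objective status of CR or sCR that is maintained on two consecutive evaluations at least 2 weeks apart"; the 27% is not described as confirmed.
- *Time on treatment.* This trial allows transplant after cycle 4 (Section 7.0); the earlier study allowed it after cycle 6 (Section 1.3).
- *Assay.* The note after Table 11.5 says daratumumab can interfere with determining complete response in some IgG kappa patients.
- *Arm B.* The plan is to "treat them with dexamethasone only for the first two cycles of treatment and then discontinue", whereas the earlier study gave dexamethasone weekly for up to twelve cycles. The 27% is a same-backbone benchmark for Arm A only.

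The first three could each put the no-effect confirmed rate below 27%.

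**Step 6: what moving the null would cost.** Keeping n = 36 and requiring ≥ 14 gives 0.081 at 27%, but power at 45% falls from 0.893 to 0.817. Restoring an error near 0.09 with power near 0.89 first becomes possible at n = 46 with ≥ 17 successes (0.0904 and 0.8941), which is 46 − 36 = 10 more evaluable patients per arm.

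**The case for a change.** The best case for a change leaves the design alone. It would add a 0.27 column (0.15) to the table and state the condition in the sentence. That costs almost nothing, removes a possible misreading, and shows the operating characteristic at the one benchmark the section cites. Imprecision in the 27%, on this view, is a reason to show more values rather than one.

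Part of this stands. Section 16.21 gives no reason for a null below its own cited rate, and the pass probability at 27% is indeed about 15%.

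The rest does not carry. The meaning of ineffective is defined in the paragraph that precedes the 9%, so the phrase has a referent. The 9% is the largest error over that null, as a significance level ordinarily is, and the first table column shows the rate to which it belongs. That readers would misread it is a guess. Showing 23% and 27% as a range of 5% to 15% would suggest more certainty than the data give, because both are point estimates from the same three-drug study. The 23% also pools phase 1 with phase 2 patients and comes from a report with 42% still on treatment.

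**Conclusion.** The concern does not call for a change. The 9% is correct for the null that the plan declares (0.0922 at 25%), and every table entry reproduces. The pass probability of 0.149 at 27% is a sensitivity value, not a corrected error rate. It assumes that the true no-effect confirmed rate in Arm A is exactly 27%, which the documents do not establish.

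An added column would leave the 36 patients, the cut-off of 13, the power of 0.89 and every analysis result as they are. It would supply a value that readers can already place between 0.09 and 0.26. Moving the null to 27% would be a real trade-off against power or sample size, and the data do not distinguish 27% from 25%.

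The consequence of a pass is also limited: Section 16.211 says only that the treatment may be recommended for further testing. Section 16.312 requires an exact 95% interval beside the estimate. At the boundary of 13/36 = 36.1% that interval is 20.8% to 53.8%, so a reader will see that both 25% and 27% remain compatible with a borderline pass. What remains is an unexplained choice of null, which a one-line reason could cover if the sponsor wishes.
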